8.1.3 Definition of Unanticipated Problems (UP)

Unanticipated problems involving risks to participants or others include, in general, any incident, experience, or outcome that meets all of the following criteria:

- Unexpected in terms of nature, severity, or frequency given (a) the research procedures that are described in the protocol-related study documents, such as the IRB-approved research protocol and informed consent document; and (b) the characteristics of the participant populations being studied;
- Related or possibly related to participation in the research (“possibly related” means there is a reasonable possibility that the incident, experience, or outcome may have been caused by the procedures involved in the research; and
- Suggest that the research places participants or others at a greater risk of harm (including physical, psychological, economic, or social harm) than was previously known or recognized

8.2 Classification of an Adverse Event (AE)

8.2.1 Severity of Event

Adverse events will be graded according to the following guidelines to describe severity:

- Mild – Events require minimal or no treatment and do not interfere with the participant’s daily activities.
- Moderate – Events result in a low level of inconvenience or concern with the therapeutic measures. Moderate events may cause some interference with functioning.
- Severe – Events interrupt a participant’s usual daily activity and may require systemic drug therapy or other treatment. Severe events are usually potentially life-threatening or incapacitating.

8.2.2 Relationship to Study Intervention

For all collected AEs, the clinician who examines and evaluates the participant will determine the AE’s causality based on temporal relationship and his/her clinical judgement. The degree of certainty about causality will be graded using the categories below:

- Definitely Related – There is clear evidence to suggest a causal relationship, and other possible contributing factors can be ruled out. The clinical event occurs in a plausible time relationship to the study intervention and cannot be explained by concurrent disease or other medications.
- Probably Related – There is evidence to suggest a causal relationship, and the influence of other factors is unlikely. The clinical event occurs within a reasonable time after the study intervention, is unlikely to be attributed to concurrent disease or other medications.
- Possibly Related – There is some evidence to suggest a causal relationship (e.g. the event occurred within a reasonable time after the study intervention). However, other factors may have contributed to the event (e.g. the participant’s clinical condition or other concomitant events). Although an AE may rate only as “possibly related” soon after discovery, it can be flagged as requiring more information and later be upgraded to “probably related” or “definitely related” as appropriate.
- Unlikely to be Related – A clinical event whose temporal relationship to the study intervention makes a causal relationship improbable (e.g. the event did not occur within a reasonable time after the study intervention) and in which other medications or underlying disease provides plausible explanations (e.g. the participant’s clinical condition or other concomitant treatments).
- Not Related – The AE is completely independent of study intervention, and/or evidence exists that the event is definitely related to another etiology. There must be an alternative, definitive etiology documented by the clinician.

8.2.3 Expectedness

The PI [name] PhD will be responsible for determining whether an AE is expected or unexpected. An AE will be considered unexpected if the nature, severity, or frequency of the event is not consistent with the risk information previously described for the study intervention.

8.3 Time Period and Frequency for Event Assessment and Follow-Up

The occurrence of an AE or SAE may come to the attention of study personnel during the study or during routine clinical monitoring following completion of the study. All AEs not meeting the

criteria for SAEs will be captured on the CRF. Information to be collected includes event description, time of onset, clinician's assessment of severity, relationship to the study intervention (assessed only by those with the training and authority to make a diagnosis), and time of resolution/stabilization of the event. All AEs occurring while on study must be documented appropriately regardless of relationship. All AEs will be followed to adequate resolution.

Any medical condition that is present at the time that the participant is screened will be considered as baseline and not reported as an AE. However, if the study participant's condition deteriorates at any time during the study, it will be recorded as an AE. UPs will be recorded in the data collection system throughout the study.

Changes in the severity of an AE will be documented to allow an assessment of the duration of the event at each level of severity to be performed. AEs characterized as intermittent require documentation of onset and duration of each episode.

The PI will record all reportable events with start dates occurring any time after informed consent is obtained until 7 (for non-serious AEs) or 30 days (for SAEs) after the last day of study participation. Events will be followed for outcome information until resolution or stabilization.

8.4 Reporting Procedures

8.4.1 Adverse Event Reporting

For any problem or AE requiring prompt reporting to the IRB but not meeting criteria for a SAE, within ten business days of the investigator becoming aware of the event, study personnel will send to the IRB a Safety Event submission in the eIRB.

8.4.2 Serious Adverse Event Reporting

The study clinician will complete a SAE Form within the following timelines:

- Immediately (within 24 hours) upon learning of an unanticipated study-related death, study personnel will notify the IRB via e-mail or fax by providing a brief summary of the event. Then, within 1 week (five business days), study personnel will send to the IRB a Safety Event submission in the eIRB.
- For a reportable SAE, study personnel will notify the IRB within five business days of the investigator becoming aware of the event. Study personnel will send a Safety Event submission in the eIRB.

All SAEs will be followed until satisfactory resolution or until the investigator deems the event to be chronic or the adherence to be stable. Other supporting documentation of the event may be requested by the IRB and should be provided as soon as possible.

8.4.3 Unanticipated Problem Reporting

Incidents or events that meet the criteria for UPs require the creation and completion of an UP report form. The PI will report UPs to the IRB. The UP report will include the following information:

Protocol identifying information: protocol title and number, PI's name, and the IRB project number;

- A detailed description of the event, incident, experience, or outcome;
- An explanation of the basis for determining that the event, incident, experience, or outcome represents an UP;
- A description of any changes to the protocol or other corrective actions that have been taken or are proposed in response to the UP.

To satisfy the requirement for prompt reporting, UPs will be reported using the following timeline:

- UPs that are SAEs will be reported to the IRB within 1 week (5 business days) of the investigator becoming aware of the event.
- Any other UP will be reported to the IRB within ten business days of the investigator becoming aware of the problem.

8.4.4 Events of Special Interest

Not applicable.

8.4.5 Reporting of Pregnancy

Not applicable.

8.5 Study Halting Rules

The study intervention will be halted when three SAEs determined to be "definitely related" or "probably related" to PPI discontinuation are identified.

8.6 Safety Oversight

Safety oversight will be under the direction of the PI who has appropriate expertise in TIPS procedures and in post procedure care. Safety oversight will occur continuously throughout the study.

9 Clinical Monitoring

Study audits may be performed to ensure that the rights and well-being of human subjects are protected, that the reported trial data are accurate, complete, and verifiable, and that the conduct of the trial is in compliance with the currently approved protocol/amendment(s). Audits may be performed at any time at the discretion of the Duke University Health System IRB.

10 Statistical Considerations

10.1 Statistical and Analytic Plans

A separate statistical analysis plan will not be created. See below for detailed description of the statistical analysis plan.

10.2 Statistical Hypotheses

Primary endpoint: The null hypothesis is that there is no difference between PPI continuation and discontinuation groups in the change in PHES pre versus post-TIPS. The alternative hypothesis is that there is a difference in the change in PHES pre versus post-TIPS in the PPI continuation and discontinuation groups:

$$H_0: \mu_{+PPI} = \mu_{-PPI} \text{ versus } H_1: \mu_{+PPI} \neq \mu_{-PPI}$$

Here μ_{+PPI} represents the mean difference in PHES among patients in the PPI continuation arm, and μ_{-PPI} represents the mean difference in PHES among patients in the PPI discontinuation arm.

Secondary endpoints:

- Per-protocol evaluation of PPI deprescribing on post-TIPS HE: The null hypothesis is that there is no difference in the change in PHES among patients who adhered with PPI discontinuation instructions versus those who continued to use PPIs.
- ITT analysis of the change in CLDQ and QOLRAD scores: The null hypothesis is that there is no difference in the pre to post-TIPS change in CLDQ/QOLRAD scores among patients in the PPI discontinuation arm compared to patients in the PPI continuation arm.
- Episodes of overt HE: The null hypothesis is that there is no difference in the number of patients experiencing an episode of overt HE, defined as a West-Haven score greater than or equal to 2, in the PPI discontinuation arm compared to patients in the PPI continuation arm.
- On-demand requirement for acid suppression therapy: Descriptive statistics will be presented on the number of patients in the PPI discontinuation arm reporting on-demand use of histamine H2 blockers or PPIs.
- Adverse events: The null hypothesis is that there is no difference in the number of patients experiencing an AE in the PPI discontinuation arm compared to patients in the PPI continuation arm.

Exploratory endpoints:

For analyses exploring the role of the microbiome in mediating PPI induced post-TIPS HE, the null hypothesis is that $b = 0$ and that $c = c'$ (no mediation, see Figure 2). The alternative hypothesis is that $b \neq 0$ and $c' < c$ (partial or complete mediation) (34).

10.3 Analysis Datasets

Analysis datasets will include all randomized patients (ITT analysis dataset) and patients who discontinued PPI therapy (defined as those who used on-demand histamine H2 blockers or PPIs less than twice weekly) versus those who continued PPIs therapy (defined as a daily dose of at least 20 mg omeprazole equivalent) (per-protocol analysis dataset).

10.4 Description of Statistical Methods

10.4.1 General Approach

- For descriptive statistics, such as patient demographics, means and ranges will be reported for continuous variables, whereas counts and percentages will be reported for categorical variables.
- For inferential tests, differences in sample means will be assessed by two-sided unpaired T-tests, whereas differences in proportions will be assessed by two-sided Fisher's exact tests.
- For statistical mediation analysis, the non-parametric bootstrap method of Preacher and Hayes will be utilized (34).
- For all inferential tests, a two-sided p-value less than 0.05 will be considered significant.

10.4.2 Analysis of the Primary Endpoint

For the primary outcome, statistical analysis will be conducted via a two-sided unpaired T-test of the hypothesis $H_0: \mu_{+PPI} = \mu_{-PPI}$ versus $H_1: \mu_{+PPI} \neq \mu_{-PPI}$. The estimate of μ_{+PPI} , the mean difference in pre versus post-TIPS PHES in the PPI continuation arm, is derived from the sample mean:

$$\bar{X}_{+PPI} = 1/n \sum (X_{post-TIPS,i} - X_{pre-TIPS,i})$$

Here $X_{post-TIPS,i}$ and $X_{pre-TIPS,i}$ are the PHES test scores 4 weeks after TIPS and 2 weeks before TIPS for i^{th} subject in the PPI continuation arm. The estimate of μ_{-PPI} is obtained in an identical fashion from patients in the PPI discontinuation arm. For the primary outcome analysis will be conducted according to the principle of ITT.

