4.2 Study Endpoints

4.2.1 Primary Endpoint

The primary endpoint of this study will be an intention-to-treat (ITT) analysis of the change in PHES pre versus post-TIPS, compared between the PPI continuation and discontinuation arms.

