7.1 Study Procedures/Evaluations

7.1.1 Study Specific Procedures

The following will study specific procedures will occur:

- Prior to randomization, all patients will undergo assessment of MHE, using the established PHES battery of pencil-and-paper tests (Figure 3), QOL assessments using the CLDQ and QOLRAD surveys, and will be provided with return-by-mail at home stool collection kits
- Patients will be randomized to either receive instructions to immediately discontinue their PPI, or to receive no specific instructions regarding their PPI
- Patients in the PPI discontinuation arm will receive intermittent phone call reminders encouraging them to refrain from PPI use, to attempt lifestyle interventions to counteract GERD symptoms (e.g. smoking cessation, avoiding late evening meals, and head-of-the-bed elevation) (40), and to use on-demand over-the-counter histamine H2 blocker therapy for intolerable GERD symptoms
- Approximately 4 weeks following TIPS creation, all patients will undergo reassessment of MHE and QOL and will be provided with return-by-mail at home stool collection kits
- At the completion of the study, all patients will be invited to resume or discontinue PPI therapy at their discretion and upon discussion with their primary care, gastroenterology, and IR physicians

Psychometric Hepatic Encephalopathy Score

Test	Description
Number connection test A (NCT-A)	Randomly dispersed numbers are to be connected with each other in serial order as quickly as possible.
Number connection test A (NCT-B)	Randomly dispersed numbers and letters are to be connected in alternating series (1-A-2-B...) as quickly as possible.
Digit-symbol	Digits from 1 to 9 are assigned respective symbols. Under each digit the corresponding symbol is to be written within a given time.
Serial dotting	Draw a dot inside each circle as quickly as possible.
Line tracing	A given line is to be traced as quickly as possible.

Figure 3: PHES tests from (41).

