7.3.2 Enrollment/Baseline

At the time of the routine pre-TIPS IR clinic visit, patients who remain potentially interested in participating in the study will meet with the study team CRC and informed written consent will be obtained from subjects who elect to participate. Baseline MHE assessment via the PHES tests and QOL surveys will then be administered and home stool collection kits will be provided.

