10.4.3 Analysis of the Secondary and Exploratory Endpoints

- Per-protocol evaluation of PPI deprescribing on post-TIPS HE: Statistical analysis will be conducted via a two-sided unpaired T-test of the hypothesis $H_0: \mu_{+PPI} = \mu_{-PPI}$ versus $H_1: \mu_{+PPI} \neq \mu_{-PPI}$. Here μ_{+PPI} and μ_{-PPI} are the pre to post-TIPS change in PHES estimated from the sample means in the per-protocol dataset.
- ITT analysis of the change in CLDQ and QOLRAD scores: Statistical analysis will be conducted via a two-sided unpaired T-test of the hypothesis $H_0: \mu_{+PPI} = \mu_{-PPI}$ versus $H_1: \mu_{+PPI} \neq \mu_{-PPI}$. Here μ_{+PPI} and μ_{-PPI} are the pre to post-TIPS change in QOL scores on the respective surveys, estimated in the ITT dataset.
- Episodes of overt HE: Statistical analysis will be conducted via a two-sided Fisher's exact test of the hypothesis $H_0: p_{+PPI} = p_{-PPI}$ versus $H_1: p_{+PPI} \neq p_{-PPI}$. Here p_{+PPI} is the proportion of patients in the PPI continuation arm experiencing at least one episode of

greater than or equal to West-Haven grade 2 overt HE, and p_{+PPI} is the corresponding proportion in the PPI discontinuation arm.

- On-demand requirement for acid suppression therapy: The proportion of patients in the PPI discontinuation arm needing on-demand histamine H2 blockers and PPIs will be reported.
- Adverse events: Statistical analysis will be conducted via a two-sided Fisher's exact test of the hypothesis $H_0: p_{+PPI} = p_{-PPI}$ versus $H_1: p_{+PPI} \neq p_{-PPI}$. Here p_{+PPI} is the proportion of patients in the PPI continuation arm experiencing at least AE, and p_{-PPI} is the corresponding proportion in the PPI discontinuation arm.
- Exploratory analysis of the role of the GI tract microbiome in mediating PPI induced post-TIPS HE: Analysis will be conducted using statistical mediation analysis (34, 43). Criteria for assessing mediation are based on the following equations:

$$Y = \mu_1 + c X + \varepsilon_1$$

$$M_j = \mu_2 + a X + \varepsilon_2$$

$$Y = \mu_3 + c' X + b M_j + \varepsilon_3$$

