10.4.6 Baseline Descriptive Statistics

Baseline characteristics of the PPI continuation and discontinuation arms will be compared, including demographics, comorbidities, prior HE and anti-HE therapy, and TIPS procedure characteristics, using means and ranges for continuous variables and counts and percentages for categorical variables. Inferential tests to assess differences in baseline characteristics of the

groups will be performed using T-tests for continuous variables and Fisher's exact tests for categorical variables.

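### Cheap improvement, not an error: the primary t-test on change in PHES is valid, but a prespecified model adjusting for baseline PHES may gain power and loses at most about 1.2 points with 20 analysed per arm

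*Combined protocol and SAP*

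**What the plan says.** The primary endpoint in 4.2.1 is an ITT "analysis of the change in PHES pre versus post-TIPS, compared between the PPI continuation and discontinuation arms". Section 10.2 states the hypothesis as equality of the two arm means, where the first mean "represents the mean difference in PHES among patients in the PPI continuation arm". Section 10.4.2 then sets the method: "For the primary outcome, statistical analysis will be conducted via a two-sided unpaired T-test of the hypothesis" of equal means, computed on each patient's post-TIPS score minus pre-TIPS score. Section 10.4.1 makes this the general rule ("differences in sample means will be assessed by two-sided unpaired T-tests"), and 10.4.3 repeats it for quality of life: "ITT analysis of the change in CLDQ and QOLRAD scores: Statistical analysis will be conducted via a two-sided unpaired T-test".

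The baselines will be in hand. Section 7.1.1 says: "Prior to randomization, all patients will undergo assessment of MHE". Section 7.3.2 adds: "Baseline MHE assessment via the PHES tests and QOL surveys will then be administered". Sections 7.3.3 and 7.3.7 place randomisation after these assessments.

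No section plans a baseline-adjusted comparison of the arms, even as a sensitivity analysis. The only regressions are the exploratory mediation models in 10.4.3, which carry no baseline term. Section 10.1 says that no separate SAP will be written, so the matter is not deferred to another document.

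**The concern.** A change score uses the baseline by subtracting it in full, which amounts to assuming that post-TIPS PHES rises one point for each point of pre-TIPS PHES. If the true slope differs from 1, part of the baseline variation stays in the change score as noise. A linear model estimates the slope instead and removes that noise.

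Precision is what is at stake. The trial has 40 patients, and 10.5 puts the lower end of its power at 71%. That section expects about 20 eligible patients a year, so extra recruitment is not an easy substitute. A covariate that is already collected is the cheapest source of precision available.

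**Working it through.** **Inputs from the documents.** 20 per arm, 1:1 allocation (10.5, 10.6.1); two-sided 0.05 (10.4.1); stated power 71% to 96% (10.5).

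**Inputs not in the documents.** SD of change, pre-post correlation (rho) and post/pre SD ratio (k). I assume rho of 0.5, 0.7 and 0.8, and k of 1, 1.1, 1.25 and 1.5.

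**1. The plan's own figure.** With no SD given, 71% to 96% cannot be reproduced forwards. Solving backwards with the noncentral t on 38 df gives a standardised difference in change of d = 0.816 for 71% and d = 1.204 for 96%. Both serve only as reference points: the percentages in 10.5 refer to individual tests, and one of these, block design, is not among the five PHES tests in 7.1.1.

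**2. Variance per patient, with pre-TIPS SD set to 1.**
- Change score: 1 + k² − 2·rho·k, which equals (1 − rho·k)² + k²(1 − rho²).
- Adjusted model: k²(1 − rho²).

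The adjusted variance is never the larger. The two are equal when rho·k = 1, that is, when the slope of post on pre is 1.

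**3. Cost of estimating the slope.** Chance baseline imbalance inflates the variance of the adjusted difference by 1 + t²/38 with t on 38 df. Its average is 1 + (38/36)/38 = 1 + 1/36 = 1.028. One degree of freedom is also lost (38 to 37).

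**4. Net variance ratio, adjusted over change score, including the 1.028.** Example with k = 1, rho = 0.5: change variance 1 + 1 − 1 = 1.00; adjusted 1 − 0.25 = 0.75; ratio 0.75 × 1.028 = 0.771. Example with k = 1.25, rho = 0.8: rho·k = 1, both variances are 0.5625, and the ratio is 1.028, the maximum under a common slope.

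| k | rho 0.5 | rho 0.7 | rho 0.8 |
|---|---|---|---|
| 1 | 0.771 | 0.874 | 0.925 |
| 1.1 | 0.840 | 0.947 | 0.995 |
| 1.25 | 0.918 | 1.008 | 1.028 |
| 1.5 | 0.991 | 1.026 | 0.979 |

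**5. Power of the adjusted model** (noncentral t, 37 df, averaged over chance imbalance). Each cell shows the result where the t-test has 71%, then where it has 96%.

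| k | rho 0.5 | rho 0.7 | rho 0.8 |
|---|---|---|---|
| 1 | 81.6 / 98.8 | 76.7 / 97.7 | 74.3 / 97.1 |
| 1.1 | 78.2 / 98.1 | 73.3 / 96.8 | 71.2 / 96.0 |
| 1.25 | 74.6 / 97.2 | 70.6 / 95.8 | 69.8 / 95.5 |
| 1.5 | 71.4 / 96.1 | 69.9 / 95.5 | 71.9 / 96.3 |

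Simulation from the 71% base (100,000 runs per cell) agrees to within about 0.3 points. Type I error was 4.8% to 5.2% for both methods.

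**6. Worst case.** With slope exactly 1, 71% falls to 69.8% and 96% to 95.5%. Over all effect sizes the largest loss is 1.2 points at 20 per arm, 1.4 at 18, 1.7 at 15 and 2.7 at 10.

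**7. Stress test without a common slope.** Suppose that decline occurs only in the continuation arm and is likelier with a worse baseline (assumed log-odds of 1 per SD), with 45% declining by 1.5 SD. At rho 0.5 / 0.7 / 0.8 the t-test has 49.9 / 65.0 / 75.6% and the adjusted model 53.2 / 64.8 / 74.4%. Across this and two similar scenarios the largest loss was 1.2 points and the largest variance ratio 1.033.

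**The case against.** The strongest reply is that this is a choice between two valid estimators with no demonstrable benefit. Nothing in the documents fixes rho or k. In half of the twelve cells above, power from the 71% base moves by no more than 1.2 points, and the stress test is close to neutral. From the 96% end of the stated range the gain is at most 2.8 points. All of this stands, and it is why the point is an improvement only. It does not remove the case for the change, because the possible loss is small and bounded while the possible gain at the lower end is about 11 points.

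Two limits also stand. The bound of about 1.2 points holds for 20 analysed per arm; 10.5 makes no allowance for dropout although 5.4.2 foresees withdrawals, so the larger losses in step 6 could apply. The per-protocol comparison and the total-effect regression in the mediation analysis would stay unadjusted; keeping the ITT t-test as a sensitivity analysis leaves each of them a like-for-like counterpart.

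A reader might also infer that adjustment settles what follows from the tests planned in 10.4.6 ("Inferential tests to assess differences in baseline characteristics of the" groups). The documents do not support that. The characteristics named there are demographics, comorbidities, prior HE and its treatment, and features of the TIPS procedure. Baseline PHES is not named, and adjusting for it does not say what to do if one of the others differs.

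**Conclusion.** The planned test stands as valid, and a baseline-adjusted model is the better prespecified choice. A reader might infer that the t-test is biased, or that chance imbalance in baseline PHES invalidates it. Neither follows: allocation is randomised 1:1, type I error is at its nominal level, and chance imbalance is already part of the sampling variance.

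Nor do the documents support a promised gain. In the range examined, the change in power runs from −1.2 to +10.6 points on a 71% base and from −0.5 to +2.8 on a 96% base, and it vanishes as rho·k approaches 1. These figures rest on assumed rho and k, a common slope, 20 analysed per arm, and effect sizes back-solved from the plan's own power. The firm part is the small downside; the upside is possible but unquantified. The change is worth making, but the validity of the trial does not depend on it.

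**What to change.** Before any outcome data are seen:

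- **10.4.2:** state that the primary ITT analysis is a linear model of change in PHES on randomised arm and baseline PHES, reporting the adjusted mean difference with its 95% CI, and that the unpaired t-test on change is a sensitivity analysis.
- **10.4.3:** use the same model for the ITT analyses of CLDQ and QOLRAD, each with its own baseline.
- **10.2:** word the hypotheses to match, as an adjusted arm difference of zero.
- **10.4.1:** add these analyses as exceptions to the general t-test rule.

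The endpoint in 4.2.1 needs no change. Because baseline is in the model, taking change or post-TIPS score as the outcome gives the same arm coefficient; only the baseline slope shifts by 1. The per-protocol comparison, whose groups 10.3 defines by drug use and not by randomisation, and the exploratory mediation models lie outside this point.

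The cost is a few sentences in four sections, one degree of freedom and about 2.8% of variance at 40 analysed patients. Both statistical costs are already in the power figures above. No additional data collection is required.
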